2. STUDY DESIGN

This is a phase II, multicenter, open-label, study of single-agent PM060184 to evaluate efficacy in patients with advanced CRC progressing after standard therapy.

Initially, 24 patients who are evaluable for the primary endpoint will be included and a futility analysis will be performed (first stage). If at least seven of these patients achieve PFS3, then the study will proceed to a second stage and 36 additional patients will be recruited.

An exploratory substudy will address pharmacogenomic and pharmacogenetic objectives. All patients who participate in the PM60184-B-002-17 clinical trial will be eligible for the substudy if they voluntarily sign a separate informed consent (IC). Refusal to participate in the substudy will not affect a patient's participation in the clinical trial.

3. OBJECTIVES AND ENDPOINTS

3.1. Primary Objective

- To evaluate the efficacy of PM060184 in terms of PFS3 in patients with advanced CRC after standard therapy.

3.2. Secondary Objectives

- To evaluate OS; PFS; overall response rate (ORR); and duration of response (DOR).
- To characterize the safety profile and feasibility of PM060184 in this population.
- To describe Peripheral Neuropathy (PN) and quality of life (QoL) profiles in this population using patient-reported outcomes (PRO) as measured by the European Organization for Research and Treatment of Cancer (EORTC) quality of life questionnaires (QLQ) for chemotherapy-induced peripheral neuropathy (QLQ-CIPN20) and general QoL (QLQ-C30).
- To characterize the Pharmacokinetics (PK) of PM060184 in this population.
- To characterize the metabolomics of PM060184, i.e. PM060184, i.e., systemic variations in the patient's pre- and post-treatment metabolic profile that allow the identification of potential biomarkers of PK, safety and/or efficacy response to PM060184.
- To characterize pharmacogenetics (PGt) of PM060184 in this population by identifying the presence or absence of germline mutations or polymorphisms that may help explain individual variability in the main PK parameters and safety outcomes.
- To characterize pharmacogenomics (PGx) of PM060184 in this population by analyzing the potential predictive factors (including BRAF-mutant-like gene expression subtypes) of sensitivity/resistance to PM060184 treatment.

3.3. Endpoints

Primary endpoint:

- Progression-free survival rate at twelve weeks, defined as the rate estimate of the percentage of patients who are alive and progression-free at 12 weeks (~3 months) after the first treatment administration.

Secondary endpoints:

- Overall Survival (OS), defined as the time from the first day of treatment to the date of death or last contact.
- Progression-free Survival (PFS), defined as the time from the first day of study treatment to the day of assessment of progression, death or last tumor evaluation.
- Overall Response Rate, defined as the percentage of patients with objective response (OR), either complete response (CR) or partial response (PR) according to the Response Evaluation Criteria in Solid Tumors (RECIST) v.1.1.
- Duration of Response, defined as the time between the date when response criteria (PR or CR, the first to be reached) are fulfilled and the first date when PD, recurrence or death is objectively documented.

- Treatment safety, including Adverse Events (AEs), Serious Adverse Events (SAEs), and laboratory abnormalities graded according to National Cancer Institute Common Terminology Criteria for Adverse Events (NCI-CTCAE) v.4. Dose reductions or delays required due to treatment-related AEs, and reasons for treatment discontinuations will also be analyzed.
- Profiles of peripheral neuropathy and quality of life as reported by patients using the EORTC QLQ-CIPN20 and QLQ-C30.
- Pharmacokinetics parameters will be evaluated in plasma by population PK modeling and/or standard non-compartmental analysis.
- Metabolomics of PM060184, i.e., intra- and inter-patient systemic variations in the patient's pre- and post-treatment metabolic profile.
- Pharmacogenetics of PM060184 will be evaluated to identify the presence or absence of germline mutations or polymorphisms that may help explain individual variability in the main PK parameters and safety outcomes.
- Pharmacogenomics of PM060184 will be evaluated to determine predictive/prognostic markers of response and/or resistance to PM060184 (including BRAF-mutant-like gene expression subtypes).

4. PATIENTS EVALUABILITY CRITERIA

Patients with relapsed, metastatic/locally advanced CRC with any KRAS-mutation status (wild-type, mutated, or status unknown), progressing after standard treatments (fluoropyrimidine, irinotecan, and oxaliplatin).

Patients must fulfill all the eligibility criteria to be eligible to participate in the study.

The study will include the following analysis population set definitions:

- “All Included Patients” analysis set is defined as all patients recorded in the database who have been included in the trial (excluding screening failures), independently of whether they have received the study drug or not.
- “All Treated Patients” analysis set is defined as all included patients who have received at least one (complete or incomplete) dose of the study drug.
- “All Evaluable Patients for Efficacy” analysis set is defined as all eligible patients who have at least one complete treatment cycle (or two PM060184 dose administrations over two cycles) and have, at least, one disease assessment at Week 6 and another one at Week 12. In addition, any patient who presents disease progression, symptomatic deterioration due to the disease or clinical progression, dies due to malignant disease, discontinues treatment due to unmanageable toxicity, or dies or discontinues treatment due to a treatment-related AE before evaluation of the response at Week 12 will also be considered evaluable for the primary endpoint and classified as a non-responder. Patients who have no disease assessment at Week 6 but remain on treatment and are assessed at Week 12 (or later, and with no evidence of disease progression) will be considered evaluable for efficacy. Patients who refuse further treatment before Week 12 due to reasons other than related AEs not considered unmanageable toxicity will be replaced.

- “All Responder Patients” analysis set is defined as all evaluable patients for efficacy who have had CR or PR as overall best response according to the RECIST v.1.1.
- “All Evaluable Quality of Life (QoL)” analysis set is defined as all patients who have fulfilled the EORTC-QLQ-C30 and EORTC-QLQ-CPIN20 questionnaires for at least two timepoints, one at baseline and at least one after the start of the therapy.

Patients must be replaced if they are considered not evaluable for efficacy for the primary endpoint (PFS3), i.e., if they are withdrawn from the study due to significant clinical deterioration of unknown reason, hypersensitivity reactions, unrelated AEs without any tumor assessments after the start of study treatment, if they refuse further treatment before Week 12 due to reasons other than related AEs not considered unmanageable toxicity, if they receive less than one complete treatment cycle (at least two PM060184 dose administrations over two cycles unless treatment discontinuation was due to unmanageable toxicity), or do not have the disease assessment at Week 12 (except in the cases outlined above).

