7.2 PATIENT REGISTRATION

Eligibility will be checked before registration confirmed by the Sponsor. The patient will be a screening failure if not all inclusion criteria are met, if any exclusion criterion is met, or if the Sponsor does not approve registration. Regardless of circumstances, Investigators will not be allowed to treat any patient before appropriate receipt of the Sponsor's agreement to proceed with registration. A patient should only be treated if eligibility criteria are still met according to assessments performed closest to first drug administration.

A patient who has been treated without the Sponsor's agreement may not be considered evaluable for the primary endpoint of the study and may need to be replaced (although can continue in treatment provided this does not pose a risk to the patient until discontinuation for any other reason).

For patients included in the study (all registered patients) but never treated, only baseline and off-study visit modules of the e-CRF should be completed but serious adverse events (SAEs) occurring during screening need to be reported (using paper SAE forms).

For screen failures (patients who started screening but were not finally registered), only the screening form of the e-CRF should be completed but SAEs occurring during screening need to be reported (using paper SAE forms).

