8. STUDY EVALUATIONS

8.1 EFFICACY

Patients will be evaluable for efficacy if they receive at least one complete treatment cycle (or two PM060184 dose administrations over two cycles) and have, at least, one disease assessment at Week 6 and another one at Week 12.

In addition, any patient who presents disease progression, symptomatic deterioration due to the disease or clinical progression, dies due to malignant disease, discontinues treatment due to unmanageable toxicity, or dies or discontinues treatment due to a treatment-related AE before evaluation of the response at Week 12 will also be considered evaluable for the primary endpoint and classified as a non-responder.

Patients who have no disease assessment at Week 6 but remain on treatment and are assessed at Week 12 (or later, and with no evidence of disease progression) will be considered evaluable for efficacy.

Patients who refuse further treatment before Week 12 due to reasons other than related AEs not considered unmanageable toxicity will be replaced.

A futility analysis will be performed once the first 24 evaluable patients complete the Week 12 (\pm 5 days) tumor assessment; progress; die due to PD; or discontinue treatment due to unmanageable toxicity (whichever occurs first). If seven patients or more achieve PFS3, then 36 additional patients will be recruited (second stage).

Tumor assessment will be measured using RECIST v.1.1 ([17](#)).

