4.2. Efficacy Populations

The “All evaluable patients for efficacy” analysis set will be used for the primary endpoint analysis of PFS3 and secondary endpoint analyses of OS, PFS and ORR.

The secondary endpoint analysis of DOR will be based on the “All responder patients”.

The “All evaluable QoL” set will be used for the secondary endpoint analysis of changes in patients QoL.

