10.1. Patient Disposition

Patient disposition analysis will be based in the “All included patients” population.

Table 10.1.1 Number of patients included, treated and evaluable for the main endpoint.

	N	%
Included patients		
Eligible patients*		
Treated patients		
Evaluable patients for efficacy		

(*) Patients meeting all inclusion criteria and not meeting any exclusion criteria.

Listing 10.1.2 Patients who do not meet all inclusion criteria or meet any exclusion criteria.

Patient id.	Criterion number(s) and description

Listing 10.1.3 Screening failures.

Patient	Inclusion/Exclusion criterion not met

Listing 10.1.4 Non-evaluable patients for efficacy.

Patient id.	Reason

Listing 10.1.5 Non-evaluable patients for safety (Non-treated patients).

Patient id.	Reason

Table 10.1.6 Patients accrual by country/institution.

Country/Institution	No. of patients included		No. of patients treated	
	N	%	N	%
Institution 1				
Institution 2				
...				

Table 10.1.7 Relevant study dates.

	Total
Date of first patient's informed consent	
Date of first dose of the first patient	
Date of last patient's informed consent	
Date of first dose of the last patient	
Date of last dose	
Date of last follow-up*	

(*) Last follow-up, examination or procedure before clinical cut-off or study closure.

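### The SAP limits one route into the PFS3 efficacy set to eligible patients; the protocol does not, and the SAP's early-failure route does not repeat the limit

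*SAP*

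**What the plan says.** Protocol 8.1 defines evaluability by treatment received and disease assessments: "Patients will be evaluable for efficacy if they receive at least one complete treatment cycle", or two doses over two cycles, with assessments at Weeks 6 and 12. The synopsis agrees. Neither mentions eligibility.

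SAP section 4 takes over this paragraph but changes its opening. The set "is defined as all eligible patients who have at least one complete treatment cycle". The following sentence opens a second route: "In addition, any patient who presents disease progression, symptomatic deterioration due to the disease or clinical progression", along with disease death, unmanageable toxicity, and treatment-related death or discontinuation before the Week 12 evaluation. These patients count as non-responders. The word 'eligible' is not repeated there, nor in the sentence on patients who missed the Week 6 assessment.

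SAP 4.2 states that this "analysis set will be used for the primary endpoint analysis of PFS3 and secondary endpoint analyses of OS, PFS and ORR". It therefore supplies the counts for the 7-of-24 futility rule and the 25-of-60 final rule.

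The footnote to SAP Table 10.1.1 defines eligible patients: "Patients meeting all inclusion criteria and not meeting any exclusion criteria". The table counts eligible, treated and evaluable patients on separate lines. Listing 10.1.2 covers "Patients who do not meet all inclusion criteria or meet any exclusion criteria", and screening failures have their own Listing 10.1.3.

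**The concern.** The two documents define different primary analysis sets. The SAP's own tables and listings foresee included patients who turn out to be ineligible, so the added word can change who is counted.

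Its scope is also unclear. Attached only to the first route, it treats ineligible patients differently according to their outcome. Attached to every route, it removes them all. The text does not say which is meant, who judges eligibility, when, or whether that person knows the outcome. In an open-label single-arm trial the PFS3 result may be known when a patient is found ineligible. The decision is a count against a fixed cut-off, so one patient can matter.

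**Working it through.** **Inputs from the documents (Protocol 9.3; SAP 5.1, 5.2).** p0 = 0.30, p1 = 0.50, one-sided alpha 0.025, power 90%, null variance in the test, 60 evaluable patients, success if at least 25 reach PFS3, continuation if at least 7 of 24.

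**Step 1: reproduce the design.**
- n = [1.960·√(0.3·0.7) + 1.2816·√(0.5·0.5)]² / 0.2² = 59.2, so 60.
- Critical count = 60·[0.3 + 1.960·√(0.21/60)] = 24.96, so 25.
- Normal-approximation power at n = 60: 0.904.
- Exact binomial for at least 25 of 60: alpha 0.0362, power 0.9225. With the 7/24 stop: 0.0355 and 0.9181.

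The plan's figures are reproduced. The exact alpha exceeds 0.025 because the cut-off comes from a normal approximation; that is separate from the present point. Deleting 'eligible' changes neither 60 nor 25, only who is counted.

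**Step 2: literal reading, set refilled to 60.** Assumptions: a fraction q of treated patients is ineligible, independently of outcome; ineligible successes leave; ineligible failures stay through the second route. The PFS3 rate in the set becomes

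p* = (1 − q)·p / [(1 − q)·p + (1 − p)].

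For q = 0.05 and p = 0.50, p* = 0.475/0.975 = 0.4872.

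| Assumed q | p* under 0.30 | Exact alpha | p* under 0.50 | Exact power |
|---|---|---|---|---|
| 0 | 0.3000 | 0.0362 | 0.5000 | 0.9225 |
| 0.02 | 0.2958 | 0.0307 | 0.4949 | 0.9105 |
| 0.05 | 0.2893 | 0.0236 | 0.4872 | 0.8894 |
| 0.10 | 0.2784 | 0.0146 | 0.4737 | 0.8447 |

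These ignore the futility stop. Including it changes little: power is 0.8842 at 5% and 0.8388 at 10%.

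**Step 3: removed patients not replaced, count of 25 kept.** Ineligibility is not among the replacement reasons in Protocol 6.3.4 or SAP section 4. Taking removals as unrelated to outcome:

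| Evaluable n | Exact alpha | Exact power |
|---|---|---|
| 59 | 0.0293 | 0.904 |
| 58 | 0.0234 | 0.882 |
| 57 | 0.0185 | 0.855 |
| 55 | 0.0111 | 0.791 |

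**Step 4: single results near the boundary,** with z = (x/n − 0.3)/√(0.21/n).
- 25/60 gives z = 1.97 and meets the rule. One ineligible success removed gives 24/59, z = 1.79: not rejected.
- 24/60 gives z = 1.69: not rejected. If the word governs every route and three ineligible failures leave, 24/57 gives z = 1.99, above 1.96, but the count of 25 is still not reached. The test and the stated rule then disagree.

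**The case against.** The strongest reply is that few patients would be affected. Protocol 7.2 requires an eligibility check and the sponsor's agreement before registration, and treatment only if criteria are still met at the assessments closest to the first dose. Protocol 6.4 does not authorize deviations bearing on the risk/benefit evaluation, and names eligibility deviations among them. Exclusions would be visible in Listings 10.1.2 and 10.1.4 and ICH listing 16.2.3. SAP 6.2.2 plans a PFS sensitivity analysis in all treated patients, and Table 11.3.7 reports PFS at 3 months from it. All this stands, and it limits the likely size. It does not settle which set is primary. That 3-month figure is a Kaplan-Meier estimate, not the binomial PFS3; no sensitivity analysis of PFS3 itself is planned.

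The protocol is also not wholly silent. Section 6.4 links eligibility deviations to trial objectives, and 7.2 says that a patient treated without the sponsor's agreement "may not be considered evaluable for the primary endpoint of the study and may need to be replaced". But 6.4 attaches no exclusion from analysis, and 7.2 is discretionary and limited to that one case. Neither amounts to a general eligibility filter.

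A reader might go further and infer that ineligible failures drop out and are replaced, so that 24/60 could be turned into 25/60 and the drug declared active. The documents do not support this. The second route keeps early failures of any patient. Only a progression first seen at the Week 12 scan itself could arguably fall outside it. Even if the word governed every route, removing failures alone leaves 24 successes, short of 25; reaching 25 would need a success among replacements that the replacement rules do not list.

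**Conclusion.** The conflict between protocol and SAP is real, and it sits in the primary analysis set. On the literal wording it works against the drug: at an assumed 5–10% ineligible, about 3 to 8 percentage points of exact power are lost (0.92 to 0.89–0.84), with a matching fall in alpha. This assumes that ineligibility is unrelated to outcome, that all ineligible failures enter by the second route, and that the set is refilled to 60. With very few ineligible patients the average effect is small, though a result at the boundary could still change on one patient. If the word governs all routes, the direction cannot be stated in advance. It does not follow from the documents that every ineligible treated patient leaves the denominator, or that the rule favours a positive result. The point is worth correcting because the ambiguity leaves room for exclusions made with the outcome known, and removing it is nearly free.

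**What to change.** Delete 'eligible' from the definition of the efficacy set in SAP section 4, so that it matches Protocol 8.1. Keep Listing 10.1.2 as planned. Add a PFS3 sensitivity analysis that excludes ineligible patients whatever their outcome.

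The cost is one word and one extra table. The sample size of 60 and the cut-offs of 7 and 25 are unchanged. The small downside is that a few ineligible treated patients stay in the primary set; the sensitivity analysis shows their influence.

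If the sponsor prefers to keep the condition, the SAP should apply it to every route, say who judges eligibility and when, require that judgment without knowledge of PFS3, and state whether such patients are replaced and what count applies if fewer than 60 remain. The protocol would then need the same wording.

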8.3 PATIENT REPORTED OUTCOMES

EORTC QLQ-CIPN20 and QLQ-C30 will be used to collect information on patients' self-reported QoL and neurotoxicity, targeting symptoms, functional limitations, and patient concerns specifically associated with treatment-induced PN, and potential activity impairment.

Patients will be asked to complete both QLQs at baseline, on Day 8 of each cycle, at the end-of-treatment visit.

Patients will be asked to complete the QLQ-CIPN20 (only) during the follow-up period (about every three months until start of subsequent antitumor therapy). If a patient discontinues treatment due to grade ≥ 3 PN, however, the QLQ-CIPN20 should be completed more frequently during the follow-up period (every month after EOT) until recovery to grade ≤ 2 (or until start of subsequent antitumor therapy).

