11.3. Efficacy Analysis

Efficacy analysis will be carried out on the “All Evaluable Patients” population except duration of response analysis which will be carried out on the “All Responding Patients” population and QoL analysis, which will be carried out on the “All evaluable QoL” population.

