11.3.3. QoL analyses

11.3.3.1. General QoL (QLQ-C30)

Table 11.3.17 Raw data for individual items* of EORTC QLQ-C30 over time.

	Baseline N (%)	Cycle 1 N (%)	Cycle X N (%)	EOT N (%)	Follow up N (%)
Item 1 Not at all A little Quite a bit Very much					
...					
Item 30 Not at all A little Quite a bit Very much					

(*) Could also be displayed by dichotomized scores, if appropriate, by for example grouping scores into 'Not at all' vs. 'Any extent'.

Table 11.3.18 Over time scores of EORTC QLQ-C30.

Scale / Item	Baseline Mean (StD)	Cycle 1 Mean (StD)	Cycle X Mean (StD)	EOT Mean (StD)	Follow up Mean (StD)
Global health status / QoL					
Functional scales					
Physical functioning					
Role functioning					
Emotional functioning					
Cognitive functioning					
Social functioning					
Symptom scales					
Fatigue					
Nauseas and vomiting					
Pain					
Dyspnoea					
Insomnia					
Appetite loss					
Constipation					
Diarrhoea					
Financial difficulties					

A time series chart will also be shown (see Figure 11.3.19).

See [Figure 11.3.24](#) as an example of Time serie chart to describe over time scores of EORTC QLQ-C30.

Table 11.3.20 Changes in scores of EORTC QLQ-C30 over time from baseline.

Scale / Item	Cycle 1		Cycle X		EOT		Follow up	
	Mean (StD)	p-value	Mean (StD)	p-value	Mean (StD)	p-value	Mean (StD)	p-value
Global health status / QoL								
Functional scales								
Physical functioning								
Role functioning								
Emotional functioning								
Cognitive functioning								
Social functioning								
Symptom scales								
Fatigue								
Nauseas and vomiting								
Pain								
Dyspnoea								
Insomnia								
Appetite loss								
Constipation								
Diarrhoea								
Financial difficulties								

Table 11.3.21 Changes in scores of EORTC QLQ-C30 over time (Repeated Measures Analysis of Variance).

Source	DF	Mean Square	F value	p-value

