11.3.3.2. Chemotherapy-induced Peripheral Neuropathy (QLQ-CIPN20)

Table 11.3.22 Raw data for individual items* of EORTC QLQ-CIPN20 over time.

	Baseline N (%)	Cycle 1 N (%)	Cycle X N (%)	EOT N (%)	Follow up N (%)
Item 1 Not at all A little Quite a bit Very much					
...					
Item 20 Not at all A little Quite a bit Very much					

(*) Could also be displayed by dichotomized scores, if appropriate, by for example grouping scores into 'Not at all' vs. 'Any extent'.

Table 11.3.23 Over time scores of EORTC QLQ-CIPN20.

Scale / Item	Baseline Mean (StD)	Cycle 1 Mean (StD)	Cycle X Mean (StD)	EOT Mean (StD)	Follow up Mean (StD)
Sensory scale					
Motor scale					
Autonomic scale					

A Time series chart will also be shown (see [Figure 11.3.24](#)).

Figure 11.3.24 Time series chart of mean and 95% CI for scales of EORTC QLQ-CIPN20.

[figure not shown]

Table 11.3.25 Changes in scores of EORTC QLQ-CIPN20 from baseline over time.

Scale / Item	Cycle 1		Cycle X		EOT		Follow up	
	Mean (StD)	p-value	Mean (StD)	p-value	Mean (StD)	p-value	Mean (StD)	p-value
Sensory scale								
Motor scale								
Autonomic scale								

Table 11.3.26 Changes in scores of EORTC QLQ-CIPN20 over time (Repeated Measures Analysis of Variance).

Source	DF	Mean Square	F value	p-value

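### One joint quality-of-life analysis set is used for two separately analysed questionnaires, so a patient with usable data on one is dropped if the other is missing at baseline or at every post-baseline visit

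*SAP*

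**What the plan says.** SAP section 4 defines the All Evaluable QoL set as "all patients who have fulfilled the EORTC-QLQ-C30 and EORTC-QLQ-CPIN20 questionnaires for at least two timepoints, one at baseline". The second timepoint must be post-baseline, that is, later than the first dose. The two instruments are joined by *and*, and no set for a single instrument is defined.

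SAP 4.2 says that this "set will be used for the secondary endpoint analysis of changes in patients QoL". SAP 11.3 repeats the assignment ("QoL analysis, which will be carried out on the" same set).

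The analyses themselves are separate. SAP 11.3.3.1 covers QLQ-C30 only (for example "Table 11.3.20 Changes in scores of EORTC QLQ-C30 over time from baseline"). SAP 11.3.3.2 covers QLQ-CIPN20 only (for example "Table 11.3.25 Changes in scores of EORTC QLQ-CIPN20 from baseline over time"). No planned quality-of-life table combines them.

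Protocol 8.3 sets the collection schedule: "Patients will be asked to complete both QLQs at baseline, on Day 8 of each cycle, at the end-of-treatment visit". After that the schedules part: "Patients will be asked to complete the QLQ-CIPN20 (only) during the follow-up period".

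**The concern.** Each questionnaire's tables need only that questionnaire, but entry to them depends on both. A missing QLQ-C30 can remove a valid neuropathy change score, and a missing CIPN20 can remove a valid general quality-of-life score. No planned analysis uses the joint condition.

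The set also does not match the schedule. CIPN20 continues alone into follow-up, and Table 11.3.25 has a follow-up column. A patient whose only post-baseline form is a follow-up CIPN20 has a change score that belongs in that column but cannot meet the set definition.

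What is at stake is the completeness of the tables for a secondary objective, the patient-reported neuropathy and quality-of-life profiles (Protocol 3, SAP 3.2). Sensory neuropathy is described as the drug's principal dose-limiting toxicity (Protocol 1.2.2), so the CIPN20 tables are the ones where avoidable loss is least welcome.

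**Working it through.** The plan states no sample size, power or completion rate for quality of life, so there is no figure of its own to reproduce. The check has three parts.

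**1. Is the joint rule relaxed anywhere?** SAP 4 sets the rule, and SAP 4.2 and 11.3 apply it. SAP 6.2.2.1 and Protocol 9.7 describe the methods without naming another population. SAP 8.13 leaves missing values out of calculations, which does not bring back an excluded patient. No exception was found.

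**2. Who is excluded?** Call a *usable pair* a baseline form plus at least one post-baseline form of the same instrument.

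| Patient has | Joint set | Own-instrument set |
|---|---|---|
| Usable pair on both, some visits missed | in | in for both |
| Usable CIPN20 pair; QLQ-C30 missing at baseline | out | in for CIPN20 |
| Usable CIPN20 pair; QLQ-C30 missing at every post-baseline visit | out | in for CIPN20 |
| Baseline forms, then only a follow-up CIPN20 | out | in for CIPN20 |
| No post-baseline form of either | out | out |

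The second and third rows also apply with the instruments exchanged. The first row assumes that the two instruments' post-baseline forms may come from different visits; the SAP does not say.

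**3. How many patients could this be?** Inputs, all assumptions except the source of N:
- N = 60, borrowed from the efficacy-evaluable target in SAP 5.1. The quality-of-life set is drawn from all patients, so the true base may be larger, or about 24 if the trial stops after its first stage. The loss scales in proportion to N.
- m = fraction without a usable pair, taken as equal for both instruments, at 5%, 10% and 15%.

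Extra loss from one instrument's analysis = N × [P(that instrument usable) − P(both usable)].

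- Fully shared missingness: P(both) = 1 − m, so the loss is 0.
- Independent: P(both) = (1 − m)², so the loss is N × m(1 − m).
- Least overlap: P(both) = 1 − 2m, so the loss is N × [(1 − m) − (1 − 2m)] = N × m.

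| m | Own-instrument set, 60(1−m) | Loss, shared | Loss, independent | Loss, least overlap |
|---|---|---|---|---|
| 5% | 57 | 0 | 60 × 0.05 × 0.95 = 2.85 | 60 × 0.05 = 3 |
| 10% | 54 | 0 | 60 × 0.10 × 0.90 = 5.4 | 60 × 0.10 = 6 |
| 15% | 51 | 0 | 60 × 0.15 × 0.85 = 7.65 | 60 × 0.15 = 9 |

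Independence is a middle case. The upper bound is 60m.

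**The case against.** The best defence is that the rule rarely bites. Only one post-baseline timepoint is needed, and both forms are due on Day 8 of every cycle and at end of treatment. A missed visit normally means that both forms are missed, which puts the loss near zero. This stands, and it is why the point is minor.

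Three stronger readings are tempting, and the documents do not support them.

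- *Any incomplete questionnaire removes the patient.* It does not. One missed form among several visits excludes nobody, and *fulfilled* is undefined, so the SAP does not say that a form with missing items fails.
- *The rule preferentially loses early stoppers.* A patient who stops early and misses Day 8 and end of treatment has no on-treatment form of either kind, so most of that loss would also occur with separate sets. The effect is clear only for a narrow group: baseline CIPN20 done, every Day 8 and the end-of-treatment form missed, no new antitumor therapy, then a follow-up CIPN20. Protocol 7.5 makes this possible, since missing the end-of-treatment visit through deterioration or for personal reasons is not a deviation. No number can be put on it.
- *Neuropathy data are lost to the report.* They leave the quality-of-life tables only. Graded neuropathy is reported as adverse events on all treated patients (SAP 4.3, 12.2), and both questionnaires are listed in SAP Appendix II.

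It could also be argued that a common set lets both instruments describe the same patients. The SAP does not give that reason and plans no analysis that uses it.

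**Conclusion.** The point holds as a small, avoidable flaw in a set definition. As written, the joint rule can exclude a patient with a usable pair on one instrument from that instrument's tables, and nothing elsewhere restores the patient. It always excludes the patient whose only post-baseline form is a follow-up CIPN20.

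The size is unknown from the documents. With 60 patients and equal missingness of 5% to 15% per instrument, the extra loss per analysis is 0 to 9 patients. Shared visits make the lower part of that range plausible. The objective is descriptive, the comparisons are exploratory at the 0.05 level, and PFS3 and its decision rule are untouched.

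**What to change.** In SAP section 4, replace the joint set with two: *Evaluable for QLQ-C30* and *Evaluable for QLQ-CIPN20*. Each requires a baseline form and at least one post-baseline form of that instrument only, and follow-up forms count for CIPN20. In SAP 4.2 and 11.3, assign each set to its own tables (11.3.17 to 11.3.21 for QLQ-C30, 11.3.22 to 11.3.26 for CIPN20).

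In the same edit, state what *fulfilled* means when some items are missing. The follow-up columns in the QLQ-C30 tables should also be checked, since the protocol does not collect that form then.

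The cost is SAP wording and one extra population flag. Trial conduct, data collection and the primary analysis do not change.
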